## STUDY OBJECTIVES

### Primary Objective

To evaluate the efficacy of administration of nitrofurantoin prophylaxis after catheter discontinuation for the prevention of catheter-associated urinary tract infections in patients with postoperative short-term catheterization following pelvic reconstructive surgery. The primary outcome will be the treatment of clinically suspected and/or culture-proven UTI within 30 days of surgery.

### Secondary Objectives

1. To evaluate adverse outcomes related to study medications in each group
2. To evaluate medication compliance

## BACKGROUND

Urinary tract infections (UTI) are the most common hospital-acquired infections, accounting for nearly 30% of cases of nosocomial infections and affecting nearly 1 million people per year. They account for nearly 8.1 million visits to health care providers and cost an estimated \$1.6 billion a year in the United States alone.

Following pelvic reconstructive and urinary incontinence surgery, UTIs are one of the most common complications. The baseline risk of UTI associated with pelvic floor surgery ranges between 5-35%, increasing greatly with catheterization. In women who are undergoing surgery for urinary incontinence, the risk of UTI ranges between 8.9% to 34%. Risk factors for urinary tract infections in women undergoing pelvic floor and urinary incontinence surgery include: history of recurrent UTI, longer operative times, and increased duration of postoperative catheterization.

Postoperative voiding dysfunction and incomplete bladder emptying is common following pelvic reconstructive and incontinence surgeries, with incidence ranging from 2.5 % to 31%. As a result, these women may have additional catheterization for a short period of time, which increases the risk of UTI. There is a 15-20% risk of developing a postoperative UTI with short-term catheterization, even if the catheter remains in place for merely 24 hours. The risk of UTI increases 5-10% each day the catheter is left in place. In the SISTEr trial, which was a multicenter, prospective, randomized trial comparing Burch colposuspension versus autologous fascial slings for the treatment of stress urinary incontinence, catheter usage postoperatively for incomplete bladder emptying resulted in an increased rate of UTIs. Participants who underwent the fascial sling (48%) had more UTI events (305) compared with the 32% of women in the Burch colposuspension group (203) ( $p < 0.001$ ).

This was concluded to be secondary to the prolonged need for catheterization due to postoperative voiding dysfunction.

Complications of catheter-associated UTI can include pyelonephritis, renal disease, and bacteremia. These complications increase the morbidity of the patients undergoing these surgeries, especially in those who are elderly. The number of pelvic floor and urinary incontinence surgeries is expected to increase by 40% in the coming years; thus, it is imperative to target efforts to reduce the risk of postoperative UTI and its complications in the elderly population.

Numerous studies have been conducted to evaluate different prophylactic antibiotic regimens to help decrease the rate of postoperative catheter-associated UTIs. Many of these studies have shown precedent for the use of antibiotic prophylaxis. In a randomized, double-blind, placebo controlled trial by Van der Wall et al., they reported on the efficacy of ciprofloxacin in preventing UTI in short-term catheterization following surgery. In their study, 20% of placebo patients had symptomatic UTIs, compared with 5% UTI rate in the ciprofloxacin treated group. Ghezzi et al. also demonstrated favorable results using single dose prulifloxacin to reduce the rate of UTI in women with short-term postoperative catheterization after undergoing a transvaginal tape procedure. In this prospective trial, no women in the prulifloxacin treatment group had a positive urine culture ( $p < 0.0001$ ), symptomatic UTI at catheter removal ( $p = 0.0015$ ) or a positive urine culture at 1 week follow-up ( $p = 0.2$ ).

In addition to fluoroquinolones, nitrofurantoin has also been evaluated as a prophylactic regimen for use with short-term catheterization. In her prospective, multicenter randomized controlled trial, Rogers et al. demonstrated that the daily use of nitrofurantoin crystals decreased risk of UTI in patients undergoing pelvic organ prolapse (POP) or urinary incontinence surgery when compared with placebo in those patients who had an indwelling suprapubic catheter postoperatively (46% versus 61%,  $p = 0.002$ ). Jackson et al. echoed these findings and found that a short 3-day course of nitrofurantoin twice daily after outpatient mid urethral sling surgery also significantly reduced the incidence of UTI in the first 6 weeks postoperatively in patients who were discharged with short-term catheterization (placebo 32% versus 17.6% in the nitrofurantoin group,  $p = 0.04$ ). Conversely, Dieter et al. found that prophylactic once daily nitrofurantoin during catheterization did not decrease the risk of urinary tract infection in patients receiving short-term catheterization following POP or urinary incontinence surgery. This finding was thought to be secondary to differences in study design leading to a lower baseline prevalence of UTI. Additionally, a Cochrane review of antibiotic prophylaxis for short-term catheter bladder drainage does find that there is some evidence, although limited, that the rate of bacteriuria is decreased with the administration of antimicrobials within the first postoperative days, or from postoperative day two until the catheter is removed.

Although there are a few studies showing favorable results for the use of prophylactic nitrofurantoin during catheterization after pelvic surgery, the optimal timing of antibiotic administration and length of dosing regimen is not well defined. The American Urological Association (AUA) recommends empiric antibiotic treatment at the time of external urinary catheter removal in patients with risk factors, such as tobacco use, advanced age, and anatomic abnormalities of the urinary tract. The AUA Panel does cite that bacteriuria in the setting of noninfectious urinary tract disease is a risk factor for bacteremia, and, thus, prophylactic antibiotic treatment at the time of catheter removal may be indicated. This recommendation is based on a few studies providing evidence for antibiotic treatment at the time of catheter removal. One of these studies, a randomized controlled trial by Harding et al., studied women with asymptomatic catheter-acquired bacteriuria after short-term catheterization and randomly assigned them to receive antibiotic therapy or no therapy at the time of Foley catheter removal. All women had urine cultures collected for up to 14 to 28 days following catheter removal. Those with antibiotic therapy demonstrated a significant increase in elimination of bacteriuria (81%) with oral antibiotics compared to the untreated population (36%). Based on these studies, the AUA does recommend empiric antibiotic treatment at the removal of an external urinary catheter in patients with risk factors. However, there is no standardization concerning the type of antibiotic to be used or treatment duration.

Although there are a few studies showing favorable results for use of nitrofurantoin during catheterization after pelvic surgery, there are no clearly defined recommendations regarding its use for urinary tract infection prevention after catheter removal. Therefore, the objective of our study is to examine the effects of administration of nitrofurantoin therapy at the time of Foley catheter removal for the prevention of catheter-associated UTI in patients undergoing POP and/or urinary incontinence surgery.

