### **Exclusion Criteria**

1. Pregnant
2. History of glucose-6-phosphate dehydrogenase deficiency
3. History of renal insufficiency, renal transplant, or nephropathy
4. Allergy to nitrofurantoin

5. History of recurrent UTI (defined as greater than two culture-proven infections in six months or three infections in one year)
6. Urinary Tract Infection (UTI) within one month of surgery
7. Non-English speaking
8. Urinary tract infection while Foley catheter is in place
9. On antibiotic therapy for other non-urological reasons
10. Sustained intraoperative bladder injury requiring prolonged catheterization greater than 5 days
11. Undergoing mesh excision from within the bladder, fistula repair, cystotomy repair, urethral diverticulectomy, sacral neuromodulation, urethral surgery, or any other procedure requiring prolonged catheterization and bladder decompression
12. Placement of a suprapubic catheter
13. Participants that request intermittent self-catheterization
14. Neurologic conditions affecting urinary tract system and normal voiding mechanisms
15. History of hepatic impairment due to prior nitrofurantoin use
16. Inability to provide consent/decisionally impaired
17. More than two in-office voiding trials

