### **Postoperative Period**

All participants will undergo a postoperative retrograde fill voiding trial per our division’s standard protocol on postoperative day zero prior to discharge (for outpatient procedures) or on the morning of postoperative day 1 for hospitalized participants.

Participants will pass the voiding trial if they void more than 200 mL with less than one-third post-void residual. If they fail, a 16 French Foley catheter will be reinserted.

All participants that fail the voiding trial will be discharged home with an indwelling Foley catheter. These participants will receive Foley maintenance education prior to discharge. They will be scheduled for a follow up voiding trial in the office in 1-7 days. The names of all participants that fail the voiding trial will be communicated to the principal investigator and/or the research nurse for continued follow up.

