### **Randomization**

Randomization will be controlled by the Carolinas HealthCare System Investigational Drug Services pharmacy through random permuted blocks and stratified per site. The biostatistician will generate the randomization sequence and provide this information to the pharmacist.

The study will be double-blinded such that both study participants and investigators will be masked to treatment allocation and block size randomization, except for the pharmacist and statistician, who will have no contact with the patients.

The Investigational Drug Services (IDS) pharmacy will provide blinded medication bottles containing either nitrofurantoin or placebo 100mg capsules. Each bottle will

contain 10 capsules. These bottles will be labeled by the IDS pharmacy with a randomization number. The study medications will be released by the pharmacy to the research nurse, who is also blinded. The medication bottles will be stored in a locked cabinet in a climate-controlled room until dispensed.

Eligible participants that have successfully passed the in-office voiding trial will be randomized into one of two groups upon completion of the voiding trial data collection sheet. There will be no indication which group the participant was randomized to. These sheets will be fluorescent colored and a part of each participant's chart. This sheet will need to be completed by the nurse administering the voiding trial.

The participants randomized to Group A will receive 100 mg nitrofurantoin every 12 hours by mouth starting on the day the Foley catheter is removed and complete a five-day course. Conversely, participants randomized into Group B will receive a matched placebo every 12 hours each day starting on the date of Foley catheter removal, for five days. Again, there will be no indication which group the participant was randomized to.

At the time of randomization, the participant will be assigned a randomization number. The bottle of medication with the same corresponding randomization ID will be dispensed. This will be a bottle of 10 capsules of nitrofurantoin or matching placebo with instructions to take every 12 hours for five days. The first dose will be given in the office. Participants will be asked to complete a one-week medication diary. Participants will be asked to return this bottle of medication, any unused medication, and a medication compliance diary at the first postoperative visit following surgery.

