Any participant that fails the in-office voiding trial will be treated per standard clinical practice. That participant will be scheduled to return for an additional in-office voiding trial in 1-7 days. They will still be eligible to participate in the study after a passed voiding trial in the office. Data will still be collected on these participants. If the participant elects to intermittent self-catheterize, they will then be excluded from the study. Any participant that required any more than two in-office voiding trials postoperatively will be excluded.

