## **STATISTICAL CONSIDERATIONS**

Calculations of sample size were based on comparisons of UTI rates in the nitrofurantoin and placebo arms. According to published results, the UTI rate in the placebo arm was 32% and approximately a 14-15% reduction was observed in the treatment arm. Using this information, we designed our study to mimic these findings, and assumed a UTI reduction rate of 18% in the nitrofurantoin arm could be observed in our clinical setting. Based on this assumption, total sample size of 164 patients was projected to achieve 80% power with a two-sided  $\alpha$  error of 0.05. We increased the total sample size to 180 to allow for a 10% dropout rate. However, due to primary investigator timeline and lack of attrition, recruitment ceased once the sample size of 164 was reached. The power was calculated by using the PASS 15 (2017, NCSS, LLC. Kaysville, Utah, USA). All analyses were conducted using an intent-to-treat principle, which included all women

randomized and not withdrawn from the study. A per-protocol analysis was also performed, and only included patients that completed the study.

Categorical data were compared using X or Fisher's Exact test where appropriate. Continuous variables were compared using Student's t-test or Wilcoxon rank sum where appropriate, and are presented as mean±standard deviation or median (interquartile range). We estimated risks for UTI with odds ratio (OR) and corresponding 95% confidence intervals (95% CI) calculated using logistic regression. A P value <0.05 defined statistical significance. All analyses were conducted using SAS Enterprise Guide version 7.1 (SAS Institute, Cary, NC). No interim analysis was performed.

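### Days of catheterisation, a named UTI risk factor known at randomisation, enters neither the stratification nor the stated analysis: a modest loss of precision, not a bias

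*Combined protocol and SAP*

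**What the plan says.** The Background gives the risk factors for UTI after this surgery as "history of recurrent UTI, longer operative times, and increased duration of postoperative catheterization". Of the three, only duration has a per-day gradient: "The risk of UTI increases 5-10% each day the catheter is left in place". The text does not say whether the 5-10% is relative or in percentage points. It also puts the risk after as little as 24 hours at 15-20%: "There is a 15-20% risk of developing a postoperative UTI with short-term catheterization".

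Under Postoperative Period, the hospital voiding trial takes place "on postoperative day zero prior to discharge (for outpatient procedures) or on the morning of postoperative day 1". Women who fail it return for an office trial 1-7 days later. Those who fail that one return after a further 1-7 days: "They will still be eligible to participate in the study after a passed voiding trial in the office". More than two office trials is an exclusion. Randomisation follows a passed office trial, when the catheter is already out.

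The Randomization section allocates "through random permuted blocks and stratified per site". Statistical Considerations compares categorical data with a chi-square or Fisher's exact test and adds: "We estimated risks for UTI with odds ratio (OR) and corresponding 95% confidence intervals (95% CI) calculated using logistic regression". No covariate is named. No section plans adjustment, stratification or a subgroup summary by catheter duration.

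**The concern.** The plan identifies a prognostic variable, lets it vary about fifteen-fold, has its value before allocation, and then does not use it. Both dates are needed to run the trial: the outcome window starts at surgery and dosing starts at catheter removal. The variable should therefore need no new data collection.

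Two things are at stake. The first is precision: the trial was sized at 80% power and recruitment stopped at 164 rather than 180, so there is little slack. The second is interpretation. The 30-day window runs from surgery, so follow-up after randomisation is 30 - 15 = 15 days for the longest duration and 30 - 1 = 29 days for the shortest. Duration therefore bears on time at risk as well as on risk, and a reader will want to see whether the arms were alike in it.

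**Working it through.** **Inputs from the documents.** Hospital trial on day 0 or 1; office trials 1-7 days apart, at most two; N = 164; placebo rate 32%; assumed reduction 18 (Statistical Considerations); gradient 5-10% per day and 15-20% risk at about 24 hours (Background).

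**Assumptions, not in the documents.** 1:1 allocation (82 per arm); hospital trial equally often on day 0 and day 1; office visits spread evenly over days 1-7; a fraction f of women needing a second office trial.

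**1. The plan's sample size.** Reading the reduction as percentage points (32% to 14%) and using the unpooled two-proportion formula:

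n = (1.960 + 0.842)² × (0.32×0.68 + 0.14×0.86) / 0.18² = 7.85 × 0.338 / 0.0324 ≈ 82 per arm, or 164 in total. The stated figure is reproduced.

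SE of the unadjusted risk difference = √(0.338/82) = 6.4 points.

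**2. Range of duration.** Shortest: 0 + 1 = 1 day. Longest: 1 + 7 + 7 = 15 days.

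**3. SD of duration.** Each even 1-7 day window has mean 4 and variance 4; the day 0/1 split has variance 0.25.

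Variance = 4 + 0.25 + 4f + 16f(1 - f).

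- f = 0: 4.25, SD 2.1.
- f = 0.30: 4.25 + 1.20 + 3.36 = 8.81, SD 3.0.

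**4. Chance imbalance.** SE of the arm difference in mean duration = SD × √(2/82): 2.1 × 0.156 = 0.33 day and 3.0 × 0.156 = 0.47 day.

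**5. Shift in the arm difference for a 1-SE imbalance.**

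- Relative reading, 5-10% of 32% = 1.6-3.2 points per day: 1.6 × 0.33 = 0.5 to 3.2 × 0.47 = 1.5 points.
- 5 percentage points per day: 5 × 0.33 = 1.6 to 5 × 0.47 = 2.3 points.

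**6. Is 10 points per day plausible?** Mean duration is 4.5 + 4f, so 4.5 to 5.7 days. Starting from 15-20% at day 1, the average risk would be 15 + 3.5×10 = 50% to 20 + 4.7×10 = 67%, against the 32% assumed. At day 15 it would be 15 + 140 = 155% or more. At 5 points per day the same sum gives 32.5% to 43.5%, already at or above 32%. These figures come from different cited sources, so this is only a plausibility check, but it rules out 10 points per day as a working slope.

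**7. Power with and without adjustment.** Simulated logistic tests, 32% versus 14%, 82 per arm, f = 0.25 (SD 2.9), 4,000 runs per row:

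| Slope (points/day) | Unadjusted | Adjusted |
|---|---|---|
| 0 | 78.8% | 78.1% |
| 1.6 | 79.4% | 78.9% |
| 3.2 | 79.3% | 80.1% |
| 5 | 79.4% | 82.7% |

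With no drug effect, the rejection rate was 4.8% to 5.3% in every row, adjusted or not.

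**The case against.** The strongest reply is that an unadjusted primary analysis of a randomised binary outcome is valid and adjustment is optional. That stands. A reader might infer that an imbalance in catheter days would bias the result or be inseparable from a drug effect. It would not bias the comparison: chance imbalance is already part of the 6.4-point SE, and the simulated error rate stays near 5%.

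A reader might also take the possible shift to be as large as 9 points. That needs a 1.96-SE imbalance (1.96 × 0.47 = 0.92 day), which about one trial in twenty would exceed, together with 10 points per day, which conflicts with the plan's own rates.

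Even 5 points per day may be too steep here. The quoted gradient describes risk while the catheter is in place, but women with a UTI during catheterisation are excluded before randomisation. The documents give no slope for UTI after removal. Longer duration also leaves less follow-up after randomisation, which could flatten the slope further.

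Two further inferences go beyond the text. The Background does not rank its three risk factors and gives no effect size for operative time, so duration cannot be called the main driver. The exclusion for "Sustained intraoperative bladder injury requiring prolonged catheterization greater than 5 days" concerns bladder injury and does not define short-term catheterisation for the trial.

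What the reply does not remove is that a named, quantified risk factor, available before allocation, appears nowhere in the stated analysis.

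**Conclusion.** The point holds as one of precision and interpretability. The 1-15 day range, stratification by site only and the absence of a duration covariate are all plain in the text. A typical (1-SE) imbalance would move the arm difference by about 0.5 to 2.3 points, against a design effect of 18 points and an SE of 6.4. The power at stake runs from a loss of under 1 point to a gain of about 3 points for slopes up to 5 points per day. N = 164 does not need to rise.

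These sizes rest on an SD of 2.1-3.0 days, 1:1 allocation and the Background gradient carrying over to UTI after removal. The documents support none of the three directly, and the last may overstate the effect.

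**What to change.** In Statistical Considerations, name days from surgery to catheter removal (continuous) as a covariate in the logistic model for UTI, and report the adjusted and unadjusted odds ratios side by side. Add a table of catheter days and number of office voiding trials by arm.

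The status of the adjusted result depends on timing. The section is written in the past tense and says recruitment has ended. The adjusted odds ratio may be primary only if that choice was fixed before outcome data were seen; otherwise it should be labelled supportive and the unadjusted result should stay primary.

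The cost is about one sentence and one table. The adjusted odds ratio is conditional on duration, so it is not directly comparable with the unadjusted one, which is why both should be shown. If duration turns out not to be prognostic, the power loss is negligible (0.7 point in the simulation at zero slope).

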## **STUDY DESIGN AND METHODS**

This is a randomized, double-blind, placebo-controlled trial offered to patients who receive postoperative short-term transurethral catheterization after undergoing surgery for pelvic organ prolapse (POP), urinary incontinence, or both. The study will be conducted at two clinical sites:

1. Women's Center for Pelvic Health (Mercy), Atrium Health, Charlotte, NC
2. Women's Center for Pelvic Health (NorthEast) Atrium Health, Concord, NC

## **Human Subject Research and Informed Consent**

Each participant will be required to sign an Internal Review Board (IRB) approved consent at the time of enrollment prior to any study-related interventions or

assessments. The informed consent form will describe the study in detail. Additionally, the study consent form will disclose the planned uses of study data, as well as potential risks to the participants. Each prospective subject will have the objectives of the study explained to them prior to enrollment. The subject will be given an opportunity to ask questions and decide whether or not to participate. Copies of the informed consent will be provided to the participants on request, and the originals will be stored at the primary study center (#1).

Subjects have the right to:

- Voluntarily participate in the study
- Withdraw or refuse participation in the study at any point without questioning
- Understand the objectives of the study
- Understand the risks and benefits of the study
- Have their confidentiality maintained

